### **BRIEF DESCRIPTION OF STUDY**

This study is a double-blind, randomized, two period crossover design. The study consists of 6 visits over a 21 week period. Fifty (50) normal healthy subjects will be treated with both Eslicarbazepine acetate (ESL, 800 mg/day) and Carbamazepine (CBZ, 800mg/day) for 6 weeks and 3 days each (maintenance 4 weeks and taper 3 days). Each antiepileptic drug (AED) treatment period will be followed by a four day taper and washout period off AED for the remainder of the month. Cognitive and behavioral function testing along with safety testing will be conducted at pretreatment baseline, the end of each randomization AED maintenance period, and after the final washout period.

### **TIME PERIOD AND NUMBER OF SUBJECTS**

A. Anticipated Number of Subjects: 50 (to obtain 30 evaluable subjects)  
B. Anticipated Duration of Study: 1 Year

### **DESCRIPTION OF MEDICATIONS**

Generic	Strength and Dosage Form	Therapeutic Classification
ESL	400 mg/capsule	Anticonvulsant
CBZ (immediate release)	200 mg/capsule	Anticonvulsant

## I. BACKGROUND AND RATIONALE

The efficacy of antiepileptic drugs (AEDs) in reducing seizures is similar for the most common type of seizures (i.e., focal +/- secondary generalized). Therefore, differential side effects play an important role in therapeutic decisions. In this regard, differential cognitive effects of AEDs are of particular interest. The older AEDs are known to produce untoward cognitive effects, which are clinically significant in some patients (Meador, 2001a). The cognitive effects of carbamazepine, phenytoin, and valproate are similar while the effects of phenobarbital are worse. Several of the newer AEDs are well tolerated and demonstrate fewer adverse cognitive effects compared to placebo and to older AEDs (Meador, 2014a, 2014b).

Eslicarbazepine acetate (ESL) is a new generation AED, which is chemically related to carbamazepine and oxcarbazepine, but is structurally different at the 10,11-position, which results in differences in metabolism. ESL is rapidly hydrolyzed to eslicarbazepine. Eslicarbazepine's main mechanism is blockade of voltage-gated sodium channels, but it also affects type T calcium channels (Hebeisen et al., 2011; Brady et al., 2011). There have been 3 phase III clinical trials: (Elger et al., 2009; Ben-Menachem et al., 2010; Sperling 2015), all with similar design in which ESL was titrated over 2 weeks and then administered for 12 weeks at 400 mg (not in one trial), 800 mg and 1.200 mg once-daily. ESL demonstrated good efficacy in adjunctive therapy for partial seizures with and without secondary generalization. However, ESL's cognitive effects in relation to the established AEDs are unknown.

Only one study has formally assessed the cognitive effects of ESL (Milovan et al, 2010). This investigation consisted of two single-blind parallel-group studies. In the first study, a single dose of 900mg of either ESL or Oxcarbazepine. This was followed by one week of placebo, then one week of ESL 800mg daily or Oxcarbazepine 300mg bid, then one week of ESL 1200mg daily or Oxcarbazepine 600mg bid. Cognitive testing was conducted pre and 3 hours post the single dose and one hour post dose at the end of each week. The total n = 56 healthy subjects with ESL (n=26) and Oxcarbazepine (n=30). The overall treatment-emergent adverse effects (especially CNS related) were greater for Oxcarbazepine. At the top doses, Oxcarbazepine had 83% of patients reporting adverse events compared to 30% for ESL; the CNS adverse reports for asthenia, dizziness, somnolence and blurred vision were greater for Oxcarbazepine. In contrast, differences between ESL and Oxcarbazepine on the cognitive measures were not significant. This disparity may be related to weaknesses in the study design. Weaknesses included small sample size, short duration of therapy, and lack of control for repeated testing (placebo tested only after the first week). The sample size was 56 (26 ESL; 30 oxcarbazepine) which may be too small to detect differences in a parallel design study; the sample size was not determined by statistical considerations. In addition, primary comparisons were for each AED to the predose in the first single dose phase "or" to the placebo phase. Direct comparisons between AEDs were done as secondary analyses. Further, the testing was conducted one hour after the morning dose of the two AEDs (e.g., ESL 1200mg and Oxcarbazepine 600mg), even though ESL would be more likely to be given qHS in the real world. This biased against ESL. Thus, this investigation does not adequately assess the cognitive effects of ESL.

The present study will investigate the cognitive and behavioral effects of ESL

compared to Carbamazepine in healthy subjects employing a double-blind, two-period, crossover design. The design provides robust statistical strength and controls for selection bias created by individual variability in cognitive performance. The use of healthy subjects will control for the effect of changes in seizure frequency on cognitive function. In addition, examining AED cognitive effects in healthy subjects allows extrapolation of the results to other patient populations treated with AEDs (e.g., psychiatric and pain disorders).

## **II. STUDY QUESTION**

What are the cognitive and behavioral effects of ESL compared to Carbamazepine in normal healthy adults?

## **III. STUDY OBJECTIVE**

The objective of this study is to determine whether there are any differences in the cognitive abilities and/or behavioral response of normal healthy volunteers after 6 weeks of treatment with ESL compared to Carbamazepine.

## **IV. STUDY DESIGN**

The study will employ a double-blind, randomized, two period crossover design. Every subject will receive each AED for 6 weeks and 3 days, which includes a one-month maintenance period and 3 day taper. Following neuropsychological assessment at the end of the maintenance phase, AEDs will be tapered off over 3 days and then the subjects will remain off drug for the remainder of 4 weeks. A study physician will monitor each subject during AED treatment periods and will adjust AED dosages with the goal of reaching therapeutic doses of ESL (800mg/day) and Carbamazepine (800mg/day). Subjects will undergo cognitive and behavioral testing at screening, prior to initiation of the first AED, at the end of each AED treatment, and at the end of each of the two washout periods. Subjects and study personnel in direct contact with subjects will be blinded to AED treatment.

## **V. STUDY POPULATION**

### **A. Number and type of subjects**

Healthy males and females between the ages of 18 and 55 who do not require concomitant medications that affect study medications or cognitive and behavioral functions. Fifty subjects will be enrolled in the study in order to complete 30 subjects.

### **B. Inclusion Criteria**

1. Healthy adults between the ages of 18 and 55 years
2. Male or female (using approved birth control methods)

3. Informed consent obtained

C. Exclusion Criteria

1. Presence of clinically significant cardiovascular, endocrine, hematopoietic, hepatic, neurologic, psychiatric, or renal disease.
2. Presence or history of drug or alcohol abuse.
3. The use of concomitant medications, which are known to affect ESL or Carbamazepine or the use of any concomitant medications that may alter cognitive function (see Section VII.E for a partial list).
4. Prior adverse reaction to or prior hypersensitivity to either study medication or to related compounds.
5. Prior participation in studies involving anticonvulsant medications.
6. Subjects who have received any investigational drug within the previous thirty days.
7. Subjects with IQ  $\leq$  70 as determined by the Peabody Picture Vocabulary Test.
8. Presence of HLA B\*1502 in subjects of Asian descent; this will be obtained at screening in subjects of Asian descent.

## **VI. STUDY PROCEDURES**

A. Overview: time and events

The study will employ a double-blind, randomized, two-period crossover design. The study consists of 6 visits over a 21 week time period. Subjects will be screened and tested at baseline, and then randomly assigned to receive each AED for 6 weeks, which includes a titration period and a one-month maintenance period. Each AED treatment period will be followed by a 3-day taper and a washout period for the remainder of 4 weeks. (See Appendix A for a complete study timetable).

B. Blinding and Controls

Subjects and study personnel will be blinded to drug randomization since all study drugs will be over-encapsulated in identical capsules.

C. Dosage Regimen

During each AED phase, subjects will be titrated onto ESL (800mg/day) or

Carbamazepine (400mg bid) and tapered off at end of 4-week maintenance according to the following schedule during each treatment arm:

Week	ESL	Carbamazepine
1	400 mg qAM + placebo	200 mg bid
2	400 mg qAM + placebo	200 mg qAM & 400mg qHS
3	800 mg qAM + placebo	400 mg bid
4	800 mg qAM + placebo	400 mg bid
5	800 mg qAM + placebo	400 mg bid
6	800 mg qAM + placebo	400 mg bid
3-day taper	400 mg qAM + placebo	200 mg bid
Stop		

The investigative team will monitor each subject's progress and safety during AED treatment periods with the goal of obtaining and maintaining ESL and Carbamazepine at dosage of 800mg/day. Subjects will remain on each AED for a total of 6 weeks (4 weeks maintenance), and then will be tapered off over 3 days followed by washout period for the remainder of 4 weeks. Total time on each drug will be 6 weeks plus 3 days. ESL will be dosed qAM and Carbamazepine will be dosed BID. The plasma  $T_{max}$  for plasma eslicarbazepine and carbamazepine will therefore approximately match the time of testing. Subjects will be tapered off AEDs over the first 3 days of each 4-week washout period according to the following schedules:

AED Dose DURING TRIAL

ESL = 800

Carbamazepine = 800

AED TAPER

400mg daily X3 days then stop

200mg bid X3 days then stop

An appropriate number of placebo capsules will be added to all AED dosages so that subjects will always take the same number of capsules for each dose given BID during AED treatment periods. Dosage times will be 8am and 8pm.

**D. Enrollment Goals**

Previous studies indicate that an enrollment of 46 subjects will be required to obtain 30 evaluable subjects. See Statistical Section for power analysis.

**E. Visit-Specific Treatment and Evaluation Sequence**

Subjects will be randomly assigned to receive both AEDs, for 6 weeks each, in a random sequence of administration. Each AED treatment period will be followed by a 3-day taper period and a 25-day washout period.

At all visits, subjects will be advised on drug compliance and avoidance of medications which may adversely effect the results of cognitive function testing. Adverse events will be documented on the appropriate case report form. Appointments will be made for follow up

visits and care will be taken to schedule all cognitive and behavioral function testing for a given subject at the same time of the day. Testing will be in the approximately 2 hours post morning dose. The time of testing and time of last 2 doses will be recorded.

The timetable for the study is listed in Appendix A. This is a visit-by-visit description of the events scheduled for each visit.

**Visit 1**      Screening Visit (-1 week prior to randomization)

Subjects will be screened to assure they meet all of the inclusion criteria and none of the exclusion criteria. All eligible subjects will be required to give informed consent. A complete history, physical examination, neurologic examination, laboratory screening including urine pregnancy test (if woman of child bearing potential), HLA B\*1502 testing for subjects of Asian descent, IQ screen with Peabody Picture Vocabulary Test, and full cognitive battery (see below) will be obtained.

**Visit 2**      Randomization- Drug Period 1 (Study week 0)

At this visit all subjects who had successfully completed all screening tests and had no significant abnormalities on baseline laboratory, physical exam, neurologic exam, or IQ testing will be randomized to study drug. At this visit, neuropsychological testing will be conducted before the first dose of study drug is administered. Subject will be randomized, and study drug will be dispensed.

**Study weeks 2 - 6**

During this period, subjects will titrate up during the 1st two weeks, and be maintained on 800mg/day of ESL or Carbamazepine during weeks 3-6. The subject's doses will be titrated according to the schedule outlined below. Telephone contacts will be made at weeks 2 and 4 to check on adverse events and to encourage compliance.

**Visit 3**      (Study week 6)

At this visit, pill bottles will be checked, and pill counts conducted. Vital signs and a brief physical examination will be obtained. In addition, antiepileptic drug blood levels, CBC and chemistries will be obtained, and cognitive function and behavioral testing will be performed. (Cognitive function and behavioral testing will be rescheduled if the subjects inadvertently used alcohol, non-approved drugs 72 hours before testing.)

**Study weeks 6 - 10**

The subject will be tapered off drug over the first 3 days and then remain off drug for the next 25 days.

**Visit 4**      (Study week 10)

This visit ends the washout period and begins the baseline for Drug Period 2. At this visit, vital signs and a brief physical examination will be obtained. Subjects will undergo cognitive and behavioral testing and then the alternate drug treatment will be dispensed. Titration will be similar to the first titrations beginning at Visit 2. In addition, a pregnancy test will be obtained in women of child bearing potential.

### **Study weeks 10 - 14**

During this period subjects will titrate up during weeks 10-12, and be maintained on 800mg/day of ESL or Carbamazepine during weeks 12-16. Telephone contacts will be made at weeks 12 and 14 to check on adverse events and to encourage compliance.

### **Visits 5 (Study week 16)**

At this visit, pill bottles will be checked, and pill counts conducted. Vital signs and a brief physical examination will be obtained. In addition, antiepileptic drug blood levels, CBC and chemistries will be obtained, and cognitive function and behavioral testing will be performed. (Cognitive function and behavioral testing will be rescheduled if the subjects inadvertently used alcohol, non-approved drugs 72 hours before testing.)

### **Study weeks 16 - 20**

The subject will be tapered off drug over the first 3 days and then remain off drug for the next 25 days.

### **Visit 6 (Study week 20)**

This visit ends the washout period and begins the baseline for Drug Period 2. At this visit, vital signs and a brief physical examination will be obtained. Subjects will undergo cognitive and behavioral testing and then the alternate drug treatment will be dispensed. Titration will be similar to the first titrations beginning at Visit 2. In addition, a pregnancy test will be obtained in women of child bearing potential.

## **VII. NEUROPSYCHOLOGICAL TESTS**

### **A. Outline:**

Note that test will performed in the following order.

Computerized Testing Battery (CNS Vitals system)

- Verbal memory immediate assessment
- Visual memory immediate assessment
- Symbol digit coding assessment

- Shifting attention test
- Dual task test
- One- and two-back continuous performance test
- Verbal memory delay assessment
- Visual memory delay assessment

Non-computerized cognitive/behavioral testing

- MCG paragraph memory-immediate recall assessment
- Symbol digit modalities test
- Stroop test
- Profile of mood states (POMS) assessment
- Columbia-Suicide Severity Rating Scale
- MCG paragraph memory-delay recall assessment

B. Description of Individual Tests:

1. Components for computerized cognitive assessments:

The computerized cognitive assessments have been used in prior studies (see reference section for CNS Vitals). It consists of verbal memory immediate assessments, visual memory immediate assessments, symbol digit coding, shifting attention tasks, dual task tests, one- and two-back continuous performance tests, verbal memory delayed, and visual memory delayed. Detailed descriptions of each are below.

1a. The order of computerized testing should be as follows:

- Verbal memory immediate
  - Encoding-30 seconds
  - Immediate recognition-1 minute
- Visual memory immediate
  - Encoding-30 seconds
  - Immediate recognition-1 minute
- Symbol digit coding  2 minutes
- Shifting attention test  2 minutes
- Dual task test  2 minutes
- One- and two-back continuous performance test  5 minutes
- Verbal memory delayed  1 minute
- Visual memory delayed  1 minute

These are actual test run times and do not include reading instructions or practice tests.

1b. Verbal memory immediate assessment:

Fifteen words are presented sequentially for 2 seconds each on the computer screen and subjects are instructed to remember the words. Following their presentation, the 15 target words are presented, and the subject indicates if the word is new (not presented) or old (a member of the original presentation list). The duration of instructions and testing is approximately 3 minutes.

Results are reported as follows:

- Correct hits (immediate)
- Correct passes (immediate)
- Total Correct hits + passes (immediate) – This is a primary measure for Z score.

1c. Visual memory immediate assessment:

Fifteen shapes are presented sequentially for 2 seconds each on the computer screen, and subjects are instructed to remember the shapes. Following their presentation, the 15 target shapes are presented, and the subject indicates if the shape is new (not presented) or old (a member of the original presentation list). The duration of instructions and testing is approximately 3 minutes.

Results are reported as follows:

- Correct hits (immediate)
- Correct passes (immediate)
- Total Correct hits + passes (immediate) – This is a primary measure for Z score.

1d. Symbol digit coding:

As a measure of processing efficiency, symbols are presented on the computer screen and the subject types in numbers that correspond to each symbol based upon a response key. The duration of instructions and testing is approximately 4 minutes.

Results are reported as follows:

- Correct responses – This is a primary measure for Z score.
- Errors
- Correct responses – Errors – This is a primary measure for Z score.

1e. Shifting attention test:

As a measure of set shifting attention and executive function, the subject assesses a series of targets and rules and responds by pressing the appropriate shift key. The duration of instructions and testing is approximately 3 minutes.

Results are reported as follows:

- Correct responses
- Errors
- Correct responses – Errors – This is a primary measure for Z score.

1f. Dual task test:

This is a test that measures multi-tasking. The subject traces the track of a target with a computer mouse while simultaneously monitoring and responding each time a number from a series of sequentially presented random numbers (ie, 1 to 99) is presented which corresponds to specific criteria (ie, between 45 and 55). The duration of instructions and testing is approximately 3 minutes. During the test portion, the level of difficulty increases by increasing the speed of the target movement. There are 8 levels of difficulty.

Results are reported for each of 8 levels (X 15 second each) of increasing difficulty as follows:

- Percent of time cursor in box
- Correct responses
- Correct average reaction time
- Commission errors

- Omission errors

Summary across the 8 levels of difficulty includes:

- Total percent of time cursor in box
- Average percent of cursor in box
- Total correct responses
- Average correct reaction time
- Total commission errors
- The primary measure for this test is a Z score averaging Z scores for (% time in box) + (Correct RT) + (# Correct – Errors).

1g. One- and two-back continuous performance test:

As a measure of working memory and sustained attention, subjects are presented a series of shapes of different colors in a sequence on the computer screen. Subjects are required to press the spacebar upon seeing the target (eg, blue square), but only when a matching stimulus (eg, blue square) appears 1 position before (ie, one-back) or 2 positions before (ie, two-back). The duration of instructions and testing is approximately 6 minutes. As an example, correct responses (yes/no) are given for the following sequence of stimuli:

- Blue square=no
- Red triangle=no
- Blue square=yes
- Blue triangle=no

Results are reported as follows:

- Correct responses
- Average correct response time
- Incorrect responses
- Average incorrect response time
- Omission errors
- The primary measure for this test is a Z score averaging Z scores for (Correct RT) + (# Correct – Errors).

1h. Verbal memory delayed assessment:

As a measure of delayed memory, subjects are presented with 15 target words from the original list used to assess immediate verbal memory interspersed with 15 foils. The subject indicates if the word is new (not previously presented) or old (a member of the original presentation list). The duration of testing is approximately 1 minute.

Results are reported as follows:

- Correct hits (delayed)
- Correct passes (delayed)
- Total Correct responses– This is a primary measure for Z score.

1i. Visual memory delayed assessment:

This is a measure of delayed memory in which the 15 target shapes from the original list are presented interspersed with 15 foils. The subject indicates if the shape is new (not previously presented) or old (a member of the original presentation list). The duration of instructions and

testing is approximately 1 minute.

Results are reported as follows:

- Correct hits (delayed)
- Correct passes (delayed)
- Total Correct responses— This is a primary measure for Z score.

2. Components for non-computerized cognitive and behavioral assessments:

The non-computerized cognitive and behavioral battery performance measures consist of MCG paragraph memory, symbol digit modalities test, Stroop test, and POMS. A detailed description of each of these follows.

2a. Peabody picture vocabulary test:

At Screening, the PPVT (third edition) will be used to assess IQ at enrollment. The PPVT is an individually-administered test of receptive vocabulary (of standard English) for children and adults from 2.5 through 90 years old. This test requires examinees to examine 4 black and white pictures and choose which best represents the meaning of a stimulus word that is presented orally by the examiner (Dunn and Dunn, 1997).

This is screening measure and is not used in analyses.

2b. MCG paragraph memory:

A MCG paragraph memory test includes a matched set of short stories that were previously developed and have been shown to be sensitive to the side effects of anticonvulsants (Meador et al, 1993). On each test day, the subjects will be read 1 of the short stories. Free immediate and delayed (15-minute) recall will be obtained.

The primary measure for Z score is the % correct for delayed recall.

2c. Symbol digit modalities test:

The SDMT is a measure of cognitive processing involving coding which is sensitive to drug effects. This is a complex graphomotor transcription task that requires the subject to transcribe symbols to numbers as quickly as possible employing a combination of direct visual identification and/or short-term memorization. Symbols with empty squares are presented, and the subject's task is to fill in the corresponding number as quickly as possible during a 90-second interval (Smith, 1973). Results are scored based on number correct in 90 seconds, which is the primary measure for Z score.

2d. Stroop test:

The Stroop test is a measure of concentration effectiveness and response inhibition. The test consists of 3 pages containing 100 items. One page contains the words "RED," "GREEN," and "BLUE" arranged randomly and printed in black ink. No word follows itself within a column. The second page contains "XXXX" written in red, green and blue ink. The final page consists of word names printed in non-congruent colors. The subject's task for the first card is to read correctly as many of the word names as possible during a 45-second interval. The second task is to read the colors of the printed "X"s as quickly as possible during an additional 45-second interval. The final task measures an interference effect by requiring the subject to inhibit the natural tendency to read the word, and to instead name the color of ink, which is incongruent with the word name. This test results in 3 scores: word, color, and word/color

contrast conditions (Golden, 1978).

The primary measure for Z score is the total # correct across all 3 conditions.

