**2e. Profile of Mood States:**

The POMS is a checklist of 65 adjectives describing mood states (Lorr et al, 1971. The subject rates the presence of each mood state in the past week on a 5-point scale from "not at all" to "extremely." The POMS is scored for 6 scales (fatigue, vigor, depression-dejection, anger-hostility, tension-anxiety, and confusion-bewilderment). All scales but the vigor scale are scored such that higher scores reflect greater mood disturbance; for the vigor scale, higher scores reflect less mood disturbance. The test is scored for each scale as well as for a total mood disturbance score derived from summing all scales (with reversal of the negatively scored items on the vigor scale). The POMS has been shown to be sensitive to AEDs in prior studies (Meador et al, 2014a, 2014b).

The Total score for POMS is the primary measure for Z score for this measure.

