### **B. Methodology for statistical analysis**

The parameters of interest are listed in Section VII. Descriptive statistics will be used to provide an overview of the primary, secondary, and other variable results. For categorical parameters, the number and percentage of subjects in each category will be presented. The denominator for percentages will be based on the number of subjects appropriate for the purpose of analysis. For continuous parameters, descriptive statistics will include number of subjects, mean, standard deviation (SD), median, minimum, and maximum. Unless otherwise specified, baseline neuropsychological data will be based on the Visit 2 assessments.

The primary outcome (pharmacodynamic) variable will be analyzed as the within subject difference between drugs in the overall neuropsychological composite Z-score for CBZ vs. ESL comparing between end of Maintenance Period scores for each drug (ie, Treatment Period 1 to Treatment Period 2). The overall composite Z-score will be computed for each condition from the individual cognitive test scores from the computerized tests and non-computerized neuropsychological tests (including the behavioral questionnaires) after transformation to Z-scores. The Z-score will be calculated using the values (mean and SD) from the average of the scores from the 3 nondrug conditions (Baseline, first Washout Period, and second Washout Period).

The primary analysis will compare the composite Z scores for ESL to Carbamazepine

for each subject at the end of the Treatment Maintenance Periods. Since the analysis is based on an overall composite score, no correction for multiple comparisons is necessary. The use of composite Z-scores avoids Type II error.

Secondary analyses will be conducted to compare the two AEDs states to the non-drug average from Visits 2, 4 & 6. The initial cognitive assessment (i.e., Visit #1) is given to reduce practice effects and will not be used in the statistical analyses. Secondary analyses will also be conducted comparing the 2 drug states to each other and the non-drug state for the individual neuropsychological variables.

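### The sole primary composite has no rule for component direction: reaction time and POMS Total enter unreversed alongside scores where higher is better

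*Combined protocol and SAP*

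**What the plan says.** Section X.B of the combined protocol and SAP makes the primary outcome the "within subject difference between drugs in the overall neuropsychological composite Z-score for CBZ vs. ESL". The composite is built from the computerized tests and the "non-computerized neuropsychological tests (including the behavioral questionnaires) after transformation to Z-scores". Standardization is defined by location and scale only: "The Z-score will be calculated using the values (mean and SD) from the average of the scores from the 3 nondrug conditions".

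Section VII.B names the score or scores that each test contributes. Three of these rules matter here:

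- Item 1f, dual task: "a Z score averaging Z scores for (% time in box) + (Correct RT) + (# Correct – Errors".
- Item 1g, one- and two-back test: "a Z score averaging Z scores for (Correct RT) + (# Correct – Errors".
- Item 2e, POMS: "All scales but the vigor scale are scored such that higher scores reflect greater mood disturbance". The total is "derived from summing all scales (with reversal of the negatively scored items on the vigor scale", and "The Total score for POMS is the primary measure for Z score for this measure".

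Every other primary measure in Section VII.B is a number correct, a percentage correct, or correct minus errors, so higher is better. Item 1d marks two symbol digit coding scores as primary: correct responses, and correct responses minus errors.

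**The concern.** A composite can be read only if its parts point the same way. Reversing vigor inside POMS makes the Total consistently higher = worse; it does not turn the Total round. Nothing in Section VII.B or X.B reverses POMS Total or reaction time at the Z stage, and nothing says whether a higher composite is better or worse. A programmer who follows the text literally would subtract harm on speed and mood from harm on everything else.

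The primary conclusion rests on this score alone, and X.B also uses the single composite as its reason for making no multiplicity correction. If signs, weights or the choice of coding score were settled after unblinding, that would be a data-dependent choice about the primary endpoint. The planned secondary analyses of individual variables could expose opposing movements but would not repair the primary test.

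**Working it through.** **1. The plan's own figure.** Section X.A gives a difference of 0.370, an SD of the difference of 0.490, two-sided alpha 0.01 and n = 30. A paired t-test with the noncentral t distribution gives 90.6% power on n - 1 degrees of freedom (90.5% on n - 2). The stated 90% reproduces.

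**2. Within the two tests, from the printed formulas.** Let every sub-score worsen by d SD. Accuracy terms move by -d and reaction time by +d.

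- One- and two-back: (+d - d)/2 = 0. Correctly oriented: -d.
- Dual task: (-d + d - d)/3 = -d/3. Correctly oriented: -d.
- POMS: Z(Total) moves by +d. Correctly oriented: -d.

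This step needs no assumption about weights across tests.

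**3. Across the composite.** The plan gives no weights, so I assume equal weight for each listed primary measure. The count is 13 if both scores in item 1d enter: immediate and delayed verbal memory, immediate and delayed visual memory, two symbol digit coding scores, shifting attention, dual task, n-back, delayed paragraph recall, SDMT, Stroop and POMS. It is 12 if symbol digit coding enters once.

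Unreversed weight, in units of one measure: 1/3 (dual task RT) + 1/2 (n-back RT) + 1 (POMS) = 1.833.

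| | 13 measures | 12 measures |
|---|---|---|
| Share of weight | 1.833/13 = 14.1% | 1.833/12 = 15.3% |
| Kept under equal harm | (10 + 1/3 + 0 - 1)/13 = 0.718 | (9 + 1/3 + 0 - 1)/12 = 0.694 |
| 0.370 becomes | 0.266 | 0.257 |
| Kept if only POMS is unreversed | (13 - 2)/13 = 0.846 | (12 - 2)/12 = 0.833 |

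**4. Power can go either way.** Assume also equal SDs of the sub-score differences and a common correlation r. The variance of the composite difference is then proportional to (1 - r)Σw² + r(Σw)², with signed weights w. For 13 measures Σw² = (10 + 3/9 + 2/4 + 1)/169 = 0.0700, and Σw is 1 if correctly signed or 0.718 as written.

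- r = 0.1: SD ratio √[(0.0630 + 0.1 × 0.5155)/(0.0630 + 0.1)] = 0.838.
- r = 0.5: SD ratio √[(0.0350 + 0.5 × 0.5155)/(0.0350 + 0.5)] = 0.740.

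Equal harm on every measure: the standardized effect is multiplied by 0.718/0.838 = 0.857 at r = 0.1 or 0.718/0.740 = 0.970 at r = 0.5. Power at n = 30 is 78% or 89%.

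Harm on RT and POMS half that on the other measures: the share kept is 10.25/12.083 = 0.848. The multipliers become 0.848/0.838 = 1.012 and 0.848/0.740 = 1.146, and power is 91% or 97%.

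**The case against.** The strongest reply is that this is an omission, not a stated error. In items 1f and 1g the plus sign may only list the scores to be averaged, and an experienced analyst would probably align signs without being told. That stands in part: a reader might infer that the plan prescribes a wrong-signed endpoint, or that the analysis will be wrong, and the documents support neither. They do not rule alignment out. But they also spell out a reversal inside POMS and none at the Z stage, so it cannot be taken as read.

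It is also fair that the plan states a direction only for POMS. That longer reaction time is worse follows from what reaction time measures. The point survives on POMS alone, which is the largest unreversed part.

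A reader might further infer that the trial is underpowered. With the SD held at 0.490, power would be 59% (13 measures) or 55% (12). That is not a supported conclusion: opposing signs also reduce the SD when components are positively correlated, and under some patterns power rises. Nor is the type I error affected: fixed signs and weights apply to both drugs within each subject.

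Finally, a reader might infer that a drug that slows people would look better on the composite. That does not follow in general, because SDMT and Stroop count correct answers within a fixed time and already have the right sign.

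**Conclusion.** The concern holds as a missing orientation rule in the sole primary outcome, whose literal reading gives reaction time and POMS Total the wrong sign. The losses inside the n-back and dual task scores, and the direction of the POMS term, follow from the scoring rules once longer reaction time is taken as worse. The composite figures (14.1% or 15.3% of the weight; 72% or 69% of the difference kept) are an illustration. They assume equal weight per measure and equal harm on every measure, and the 0.370 is borrowed from a different composite in an earlier study. The power figures rest on still more assumptions and do not determine the severity.

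This should be fixed before unblinding, because the primary score cannot be reproduced from the plan and the correction is nearly free. A separate, smaller point is that item 1d marks two overlapping scores as primary, so symbol digit coding would count twice if both enter.

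**What to change.** Before unblinding:

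- In Section X.B, state that every component Z is oriented so that higher = better before averaging, and hence that a higher composite is better.
- Item 1f: dual task = average of Z(% time in box), -Z(Correct RT) and Z(# Correct - Errors).
- Item 1g: one- and two-back = average of -Z(Correct RT) and Z(# Correct - Errors).
- Item 2e: POMS = -Z(Total).
- Item 1d: keep one primary score. Correct responses minus errors would match item 1e.
- State the weight chosen for each listed primary measure, including whether immediate and delayed memory count separately. No particular weighting is prescribed here; it only has to be fixed in advance.

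The cost is a short addition to X.B and four scoring edits, with no change to data collection, visits or number of subjects.
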